3.5.4 Per-Protocol Population

The Per-Protocol Population (PP) will include all mITT subjects who were considered compliant with study drug administration (i.e. had an adherence of at least 80%) and who had no major protocol deviations that were considered as potentially impacting the efficacy results.

Major protocol deviations might include, but are not limited to, subjects taking a not-permitted concomitant medication, the IMP not being administered during the trial as defined in the protocol, subjects receiving a treatment different than the one assigned by randomisation. Categories of protocol deviations and additional details are reported in Section 4.10. The exact definition of major protocol deviations impacting the efficacy results will be discussed by the

CONFIDENTIAL

Sponsor:	Zambon S.p.A.	Protocol Number:	Z7224L01
----------	---------------	------------------	----------

study team during the blind review of the data and described in the Blind Data Review and Analysis Sets Report.

Results of the primary and relevant secondary efficacy endpoints analyses conducted for the PP will be considered as supportive.

3.5.5 Other Populations Defined for Tables and Listings

For the purposes of tables and listings, a further 3 populations are defined:

- All screened subjects: all subjects who provide informed consent;
- Screening failure subjects: all subjects who provide informed consent and are screening failures;
- Enrolled subjects: all subjects who provide informed consent and are not screening failures.

3.6 Withdrawn Subjects

Subjects will be withdrawn from the trial for one of the following reasons:

- subject may withdraw from the study at any time at his/her own request;
- subject may withdraw from the study due to an AE including subjects experiencing a decrease in FEV₁ >15% from pre-bronchodilator baseline and/or clinically determined bronchospasm after receiving their first dose of IMP;
- subject may be withdrawn at any time at the discretion of the Investigator for safety, behavioural, compliance or administrative reasons;
- subject may be withdrawn due to lack of adherence to study medication regimen;
- subjects who become pregnant should be withdrawn from the trial;
- non-emergency unblinding of study treatment allocation;
- lost to follow-up: before a subject is deemed lost to follow-up, the Investigator or designee must make every effort to regain contact with the participant (where possible, 3 telephone calls and, if necessary, a certified letter to the participant's last known mailing address or local equivalent methods). These contact attempts should be documented in the participant's medical record. Should the participant continue to be unreachable, he/she will be considered to have withdrawn from the study;
- Sponsor, CA, or EC/IRB(s) terminate the trial or participation of an individual site.

The reason for removal of a subject from the trial or premature discontinuation of treatment must be fully documented in the electronic case report form (eCRF) as well as in respective source documents.

Any subject who withdraws after randomisation will not be replaced. Withdrawn subjects will not be re-entered into the study.

CONFIDENTIAL

Sponsor:	Zambon S.p.A.	Protocol Number:	Z7224L01
----------	---------------	------------------	----------

3.7 Randomisation

At Visit 2, eligible subjects will be randomised using the interactive web response system (IWRS) according to a pre-specified randomisation scheme such that they either receive colistimethate sodium or placebo. Site and use of stable concomitant therapy with oral macrolides (e.g. azithromycin or erythromycin or clarithromycin) (Yes/No) will be considered as factors for balancing randomisation, i.e. stratification factors. Thus, within each site, subjects with oral macrolides use will be randomised independently from subjects without use of macrolides, to receive colistimethate sodium or placebo in a 1:1 ratio. The randomisation within each site and nested level macrolide use will be done with blocks to guarantee a good balance between colistimethate sodium and placebo at any stage of the enrolment.

Note: according to Exclusion Criterion 15, the decision on whether stable concomitant antibiotic therapy with oral macrolides will be administered to a subject or not will have been taken at least 30 days prior to the Screening Visit (Visit 1). The treatment with oral macrolides should be continued throughout the trial in order not to jeopardize the study results.

3.8 Blinding

Investigational site staff including the Investigator and all personnel involved in study procedures will be blinded to treatment allocation. All Contract Research Organisation (CRO) and Zambon study staff involved in monitoring, data management, or other aspects of the study will also be blinded.

The allocation to treatment will be stored within the IWRS database until unblinding of the trial is requested.

The code for any individual subject will not be broken by the Investigator during the course of the trial except in the circumstance of a Serious Adverse Event (SAE) where knowledge of treatment assignment is essential for the management of patient care. CRO and Zambon Pharmacovigilance can unblind subjects in case of suspected unexpected serious adverse reactions (SUSARs) to be reported to the competent authority (CA) and ethics committees (ECs).

The randomisation code will be provided to the Biostatistics group once written authorization of database lock has been received and analysis populations have been defined.

3.9 Sample Size

The sample size was calculated considering the results from the previous trial (CCI [REDACTED]), relevant literature and the clinically meaningful benefit the treatment should provide. A treatment difference of CCI [REDACTED] between the colistimethate sodium and placebo groups. CCI [REDACTED]

For the purpose of the power calculation, a simulation of exacerbations was carried out by randomly assigning a patient a value CCI [REDACTED] according to the treatment group they were in and then generating a CCI [REDACTED] event rate using this parameter. This CCI [REDACTED] led to two negative binomials with the following parameter values:

Placebo: mean CCI [REDACTED], variance CCI [REDACTED]

Colistimethate sodium: mean CCI [REDACTED], variance CCI [REDACTED]

CONFIDENTIAL

Sponsor:	Zambon S.p.A.	Protocol Number:	Z7224L01
----------	---------------	------------------	----------

These are rates per year. Note that, since the variances are greater than the mean, this means that there is mild over-dispersion.

Under these assumptions, a [CCI] allowing for over-dispersion for frequency of exacerbation (FOE), with a two-sided significance level of [CCI], a treatment effect of [CCI] and a follow-up time of 1 year, assuming a frequency of [CCI] pulmonary exacerbations per annum for the FOE, a sample size of 170 completed subjects per group would provide a power of 90% (simulated in [CCI] 1). If the treatment effect size is [CCI] between the colistimethate sodium and placebo groups, the power with [CCI] completed patients per group would be [CCI].

Assuming a drop-out rate of about 20%, the total sample size should be 210 subjects per treatment group (420 total subjects).

A fully blinded reassessment of trial size and power was undertaken for Promis I based on blinded data as of 15th January 2020 in 342 randomised, ITT population subjects. This evaluation gave a blinded annualised exacerbation rate estimate of 1.024 per year and an over-dispersion estimate of 0.273. For the hypothesised [CCI] reduction in the exacerbation rate with colistimethate sodium, this translates to annual event rate estimates for placebo and colistimethate sodium of 1.2701 vs 0.8256. The current data in Promis I, therefore, suggested that $n=145$ subjects per arm (290 total, unadjusted for dropout) were required to deliver 90% power, as compared to $n=170$ subjects per arm (340 total, unadjusted for dropout) stated in the protocol. Furthermore, the smallest observed reduction in the exacerbation rate with colistimethate sodium that will yield [CCI] in Promis I was computed to be [CCI].

This recalculation of the sample size was further refined to allow for a reduced overall exposure in Promis I arising due to some subjects dropping out of the study before completing 1 year of follow-up. This leads to a requirement for $n=188$ subjects per arm (376 total, adjusted for dropout) to detect a [CCI] reduction in the event rate with 90% power as compared to $n=210$ subjects per arm (420 total, adjusted for dropout) stated in the protocol; and with $n=188$ subjects per arm, the smallest observed rate reduction to yield [CCI] was computed to be [CCI].

It was, therefore, clear from the blinded data accrued in Promis I subjects to January 2020 that the $n=210$ subjects per arm stated in the protocol was unnecessarily high. At worst, the actual number of subjects required in Promis I is $n=188$ per arm (376 total) and this is inclusive of adjustment for the actual dropout rate seen in the trial itself. Given that, at the time of this sample size reassessment, a total of $n=372$ subjects had been randomised into Promis I, it could very reasonably be argued that very few, if any, further subjects were actually required to be randomised into the study to provide the required power to test the hypothesis that inhaled colistimethate sodium significantly reduces the exacerbation rate relative to placebo. Recruitment was, therefore, concluded with 377 randomised subjects.

CONFIDENTIAL

Sponsor:	Zambon S.p.A.	Protocol Number:	Z7224L01
----------	---------------	------------------	----------

4 Statistical Methodology

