Sample Size:	A total of 420 randomised patients (210 per group) is foreseen assuming a withdrawal rate of approximately 20%, to achieve a total number of completed patients of 170 per group. For the primary endpoint of frequency of exacerbation (FOE), and a Poisson regression allowing for over-dispersion for FOE, with a two-sided significance level of 0.05, a treatment effect of 35% and a follow-up time of 1 year, with an FOE of 1.09 in the placebo group, this sample size will provide a power of 90%.

If the treatment difference effect size is 30% between the colistimethate sodium and placebo groups, the power with 170 completed patients per group will be 80%.

Population:Inclusion Criteria:

Subjects are eligible if they:

1. are able and willing to give informed consent following a detailed explanation of participation in the protocol and signed consent obtained;
2. are aged 18 years or older of either gender;
3. are diagnosed with NCFB by computerised tomography (CT) or high resolution CT (HRCT) as recorded in the subject's notes and this is their predominant condition being treated;
4. had at least 2 NCFB pulmonary exacerbations requiring oral or inhaled antibiotics or 1 NCFB pulmonary exacerbation requiring intravenous antibiotics in the 12 months preceding the Screening Visit (Visit 1) and had no NCFB pulmonary exacerbation with or without treatment during the period between Visit 1 and Visit 2;
5. have a documented history of *P. aeruginosa* infection;
6. are clinically stable and have not required a change in pulmonary treatment for at least 30 days before the Screening Visit (Visit 1);
7. have pre-bronchodilator FEV₁ ≥25% of predicted;
8. had a positive sputum culture for *P. aeruginosa* from an adequate sample taken at the Screening Visit (Visit 1) or during the screening period.

Exclusion Criteria:

Subjects are not eligible if they have/are:

1. known bronchiectasis as a consequence of cystic fibrosis (CF);
 2. known history of hypogammaglobulinaemia requiring treatment with immunoglobulin, unless fully replaced and considered immunocompetent by the Investigator;
 3. myasthenia gravis or porphyria;
 4. severe cardiovascular disease such as severe uncontrolled hypertension, ischaemic heart disease or cardiac arrhythmia and any other conditions that would confound the evaluation of safety, in the opinion of the Investigator;

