3.1 Discussion of Study Design

This is a randomised, multi-centre, double-blind, placebo-controlled, parallel-group interventional trial in subjects with NCFB suffering from chronic infections with *P. aeruginosa*.

The trial will be conducted in approximately 100 sites in up to 15 countries. A total of 420 subjects (210 in each treatment group) are planned to be enrolled into the trial. The enrolment is competitive among sites.

At Visit 2 (within 30 days after Visit 1), eligible subjects with *P. aeruginosa* cultured from an initial sputum sample will be randomised in a 1:1 ratio to receive either colistimethate sodium or placebo.

It is planned that subjects will be contacted by phone 7 days after Randomisation (Visit 2) to determine if there are any issues with IMP administration and/or any initial AEs and will, thereafter, attend 5 further visits at the sites at 1, 3, 6, 9, and 12 months after Randomisation (i.e. Visits 3, 4, 5, 6, and 7) and will have 1 follow-up phone call at 12.5 months. Additional clinic visits, where feasible, and weekly phone calls will be conducted following pulmonary exacerbations until resolution.

The maximum expected duration of participation in the trial for an individual subject, from Visit 1 (Screening) to the follow-up phone call is up to 13.5 months. Treatment duration will be 12 months.

The start of the trial is defined as first subject in, i.e. Visit 1 for the first subject. The end of the trial is defined as the last subject out, i.e. when the last subject has the follow-up phone call.

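### SAP 3.9 splits the blinded rate of 1.024 geometrically, so both stated arm rates are about 2.3% too high; n shifts by a few per arm and stopping at 377 still stands

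*SAP*

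**What the plan says.** SAP Section 3.9 describes a blinded reassessment of trial size, using data on 342 randomised subjects as of 15 January 2020. It gave a "blinded annualised exacerbation rate estimate of 1.024 per year and an over-dispersion estimate of 0.273". The SAP converts this, under the hypothesised reduction, to "annual event rate estimates for placebo and colistimethate sodium of 1.2701 vs 0.8256". The size of the reduction is redacted there, but the Protocol Summary gives the design assumptions as "with a two-sided significance level of 0.05, a treatment effect of 35% and a follow-up time of 1 year".

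From these rates the SAP concludes that 145 "subjects per arm (290 total, unadjusted for dropout) were required to deliver 90% power". It then makes the calculation "allow for a reduced overall exposure in Promis I arising due to some subjects dropping out of the study before completing 1 year of follow-up", which gives 188 "subjects per arm (376 total, adjusted for dropout) to detect a" the same reduction with 90% power. It goes on: "At worst, the actual number of subjects required in Promis I is" 188 per arm (376 in total). Recruitment closed at 377 randomised, against 420 in the protocol. SAP Section 3.1 says that subjects "will be randomised in a 1:1 ratio to receive either colistimethate sodium or placebo".

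Section 3.9 does not say how the pooled rate was divided between arms, what mean exposure lies behind 188, or whether 0.273 was estimated with the arms pooled.

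**The concern.** With equal allocation and similar follow-up by arm, a blinded rate per subject-year is the arithmetic mean of the two arm rates. The stated pair does not average back to the rate from which it was derived. Rates that are too high give too many expected events per subject, and so an n that is too small.

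These figures are the written justification for closing recruitment 43 subjects below the protocol target (420 - 377), and SAP Section 4.13 points to Section 3.9 for the reduced sample size. A reader who checks the section will find that the arm rates disagree with the pooled rate. The worst-case wording also invites the question of whether 188 survives the correction.

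**Working it through.** **Inputs.** Pooled rate 1.024, dispersion k = 0.273, arm rates 1.2701 and 0.8256, 90% power, 145 and 188 per arm, 377 randomised (SAP 3.9). Two-sided 0.05, 35% reduction, one year (Protocol Summary). Allocation 1:1 (SAP 3.1). Negative binomial primary model (SAP 4.7.4).

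**1. How the rate was split.**
- Ratio: 0.8256 / 1.2701 = 0.650, which agrees with a 35% reduction.
- 1.024 / √0.65 = 1.2701 and 1.024 × √0.65 = 0.8256. Both match to four decimals, so the split is geometric.
- Arithmetic mean: (1.2701 + 0.8256) / 2 = 1.048, and 1.048 / 1.024 = 1.023.

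**2. The pair that averages to 1.024.** Placebo = 2 × 1.024 / 1.65 = 1.241; colistimethate sodium = 0.65 × 1.241 = 0.807.

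**3. Reproducing 145.** The negative binomial Wald formula is

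n per arm = (1.960 + 1.2816)² × [(1/μ₁ + 1/μ₂)/t + 2k] / (ln 0.65)²,

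with (1.960 + 1.2816)² = 10.507 and (ln 0.65)² = 0.1856.
- Stated rates, t = 1: 10.507 × (1.9986 + 0.546) / 0.1856 = 144.1, so 145. This is the SAP's figure.
- Arithmetic split, t = 1: 10.507 × (2.0451 + 0.546) / 0.1856 = 146.7, so **147**.

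**4. With reduced exposure.** Mean exposure is not stated, so 188 cannot be reproduced independently. Solving the same formula for the t that returns 188 from the stated rates (187.01 to 188.0 before rounding up) gives t of about 0.721 to 0.725 year. At that assumed exposure:
- Arithmetic split, k = 0.273: n = 190.6 to 191.6, so **191-192 per arm** (382-384 in total).
- Power at 377 (188.5 per arm): 89.5% to 89.7%.

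**5. If 0.273 is a pooled dispersion.** A negative binomial dispersion estimated without a treatment term absorbs the difference between arms. Removing it by moments, at one year of follow-up and under the SAP's own hypothesis:
- Between-arm variance: (1.241² + 0.807²)/2 - 1.024² = 1.0958 - 1.0486 = 0.0472.
- Within-arm k = (0.273 × 1.024² - 0.0472) / 1.0958 = (0.2863 - 0.0472) / 1.0958 = **0.218**.
- n without dropout: 140.5, so **141**. At t of 0.721 to 0.725: 184.4 to 185.4, so **185-186**.
- Power at 377: about 90.5%.

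| Rates | k | n, no dropout | n, t ≈ 0.72 | Power at 377 |
|---|---|---|---|---|
| 1.2701 / 0.8256 (SAP) | 0.273 | 145 | 188 | about 90% |
| 1.241 / 0.807 | 0.273 | 147 | 191-192 | about 89.5% |
| 1.241 / 0.807 | 0.218 | 141 | 185-186 | about 90.5% |

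**The case against.** The strongest reply is that this changes very little. The figure of 145 follows exactly from the arm rates the SAP states; only the step from 1.024 to those rates is at fault. Moving from 145 to 147 is a smaller change than the choice between standard formulas: a null-variance version of the calculation gives 141 with the SAP's own rates. A 2.3% shift is also well inside the sampling error of the blinded rate. If mean exposure in the 342 subjects is assumed to be 0.5 to 0.9 year, the lower 95% limit of that rate is about 0.87 to 0.91. All of this stands.

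Two of the inputs used here are also not in the SAP: the 0.72-year exposure, and the reading of 0.273 as an unadjusted pooled dispersion. That stands too, and it is why the results after steps 1 to 3 are given as conditional.

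The worst-case phrase can fairly be read as the larger of the two figures just given, 145 and 188, and not as a statistical upper bound. On that reading it is loose wording, not a false claim.

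A reader might infer from the wrong split that 188 is too low and that the trial closed underpowered. The documents do not support that. The shortfall appears only if the rate is corrected and the dispersion is left at 0.273. If 0.273 is pooled, correcting both puts the requirement at 185-186, and 188 is slightly conservative.

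What the reply does not remove is the inconsistency itself: under 1:1 allocation, the printed arm rates do not average to the printed pooled rate.

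**Conclusion.** The concern holds in a limited form. The arm rates in SAP 3.9 come from a geometric split and are both about 2.3% too high; the consistent pair is 1.241 and 0.807. This assumes that 1.024 is events per subject-year with similar exposure in the two arms.

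The effect is +2 per arm without dropout. With dropout it is +3 to +4 per arm at the stated dispersion, or -2 to -3 per arm if 0.273 is pooled. Power at 377 lies between about 89.5% and 90.5%. The figures with dropout depend on the back-solved exposure of about 0.72 year.

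A reader might go further and conclude that 145 and 188 are invalid, or that stopping at 377 was unjustified. Neither follows: 145 reproduces from the stated rates, and power stays within about half a point of 90% under either reading of the dispersion. No planned analysis uses these rates. This is a minor correction of figures.

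**What to change.** In SAP 3.9, or in a note in the clinical trial report:

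- Restate the arm rates as 1.241 and 0.807, and n without dropout as 147 per arm at dispersion 0.273.
- State the mean exposure used to reach 188, and whether 0.273 was estimated with the arms pooled and without a treatment term.
- Replace the worst-case statement of 188 with a range of about 185-192 per arm and power at 377 of about 89.5-90.5%, conditional on that exposure and on the two dispersion values. Say that the range does not include sampling error in the blinded estimates.

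The cost is a few restated figures and two disclosures. No additional patients are needed, and the analysis does not change.

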4.1 Planned Analyses

The statistical analysis will be performed by CCI and will be carried out according to International Conference on Harmonisation (ICH) guidelines ICH E9: "Statistical Principles for Clinical Trials" (CPMP/ICH/363/96 September 1998) and ICH E10 "Choice of Control Group in Clinical Trials" (CPMP/ICH/364/96 January 2001).

All the statistical analyses and outputs will be produced using SAS release 9.4 or later or later (SAS Institute, Inc. Cary, NC, USA).

The data from all countries and all sites will be pooled and summarised. Unless stated otherwise, all available data from withdrawn subjects will be included in the analysis up to the time of withdrawal.

4.1.1 Populations for the Analysis

Demographics and baseline characteristics will be summarised for the mITT population. Demographics and selected baseline characteristics will be also presented for the Safety Population.

The following baseline characteristics will be presented on the mITT Population only:

- Smoking and Alcohol Status
- Non-CF Bronchiectasis History
- Past and Concomitant Relevant Diseases, Diagnosis or Surgeries
- Prior and Concomitant Medication

No baseline testing will be performed.

Primary and relevant secondary efficacy variables will be summarised and analysed for the mITT and PP Population. Results on PP will be considered as supportive.

The number of days of work absence and hospitalisations will be analysed for the mITT population only.

In addition, the analysis on the mean annual NCFB pulmonary exacerbation rate and the CCI will be performed considering the subgroup of mITT subjects who were considered adherent i.e. had an adherence of at least 80% (excluding partial doses of $\leq 12.5\%$ as detailed in Section 4.5.1).

The exposure data will be analysed on the Safety and mITT Populations.

The safety variables will be summarised for the Safety Population.

In case an error occurs in treatment allocation, the following rule will be followed:

- If a subject was randomised but received the incorrect treatment for all the time the subject was in the study, he/she will be reported under the randomised treatment group for all analyses performed on the ITT and on the mITT Population (and in listings on all screened subjects). He/she will be reported under the treatment actually received for

CONFIDENTIAL

Sponsor:	Zambon S.p.A.	Protocol Number:	Z7224L01
----------	---------------	------------------	----------

all analyses performed on the Safety Population (i.e. an as-treated analysis will be performed). Such subjects will be excluded from the PP Population.

- If a subject received the incorrect treatment after being treated with the correct one, it's foreseen that the subject will be withdrawn from the study. Data for this subject will be analysed until the date of the wrong treatment dispensing. All the data collected after that date will be reported in listings and flagged, but not included in the summary statistics. He/she will be reported under the randomised treatment group for all analyses performed and listings presented.

